6.2.5 Definitions of dose limiting toxicities (DLTs)

A dose-limiting toxicity (DLT) is defined as an adverse event or abnormal laboratory value assessed as unrelated to disease progression, inter-current illness, or concomitant medications that meets any of the following criteria in [Table 6-3](#).

For the purpose of dose escalation decisions, only DLTs occurring during the first 6 weeks of study treatment will be necessarily considered and included in the BLRM.

[figure not shown]
Toxicity will be assessed using the NCI Common Terminology Criteria for Adverse Events, version 4.03 (evs.nci.nih.gov/ftp1/CTCAE) unless otherwise specified.

The investigator must notify the Sponsor immediately of any unexpected CTCAE grade ≥ 3 adverse events or laboratory abnormalities. Prior to enrolling patients into a higher dose level, CTCAE grade ≥ 2 adverse events will be reviewed for all patients at the current dose level.

For toxicities which, by definition, require a time-window in order to be defined as DLTs (grade 3 non-hematologic toxicity for ≥ 7 consecutive days), a subsequent visit and/or laboratory assessments must be scheduled accordingly. For example, if a grade 3 non-hematologic toxicity is observed, it must also be observed at least 7 days later, with no intervening lower grades, in order to qualify as a DLT.

Table 6-3 Criteria for defining dose-limiting toxicities

| TOXICITY | DLT CRITERIA |
|---|--|
| Hematologic | |
| Blood and lymphatic system disorders | Neutropenia CTCAE Grade 4* |
| | Febrile neutropenia CTCAE Grade ≥ 3 (ANC $< 1.0 \times 10^9/L$ + Fever ≥ 38.5 degrees C) |
| | Thrombocytopenia CTCAE Grade 4 (Platelets $< 25 \times 10^9/L$)* |
| | Hemorrhagic Event CTCAE Grade ≥ 2 |
| | Anemia CTCAE Grade 4 for ≥ 7 days despite PRBC transfusions |
| Non-Hematologic | |
| Gastrointestinal disorders | Vomiting CTCAE Grade ≥ 3 for > 7 days in duration |
| | Nausea CTCAE Grade 3 despite the use of anti-emetic therapy |
| Hepatic | Total bilirubin CTCAE Grade ≥ 3 , with Direct Bilirubin ≥ 0.5 mg/dL |
| | AST/SGOT or ALT/SGPT CTCAE Grade 3 for ≥ 5 consecutive days |
| | AST/SGOT or ALT/SGPT CTCAE Grade 4 |
| CK elevation | CTCAE Grade ≥ 3 |
| Other | Any CTCAE Grade 3 non-hematologic toxicity for ≥ 7 days Any CTCAE Grade 4 non-hematologic toxicity |
| CTCAE version 4.03 will be used for all grading. | |
| * In two consecutive assessments (the second assessment will be considered valid and final) | |

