Appropriate eligibility criteria and specific DLT definitions, as well as specific dose modification and stopping rules are included in this protocol.

Patients who experience a DLT will have their therapy with LDE225 and INC424 interrupted and will be followed as described in [Table 6-4](#). After recovery from the toxicity in question, if the Investigator believes that it is in the patient's best interest to resume therapy with LDE225 and INC424, the patient may resume therapy, only after consultation with the Sponsor, according to the guidelines described in [Section 6.3.1](#) and [Table 6-4](#).

However, the patient must be permanently discontinued from study medication and withdrawn from the study, if any of the following DLTs occur:

- any grade ≥ 3 hemorrhagic event
- grade 4 anemia for ≥ 7 consecutive days despite PRBC transfusions
- 2nd episode of grade ≥ 3 febrile neutropenia
- grade 3 renal toxicity for ≥ 7 consecutive days
- grade 4 renal toxicity
- grade 4 non-hematologic toxicity

If during the first 6 weeks a patient misses > 10 doses of LDE225 or > 20 doses of INC424, the patient will not be evaluable for DLTs. The patient can continue in the study, but another patient has to be enrolled at the same dose level in order to reach the required minimum number of patients in the cohort.

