| > 2.0 – 3.0 x ULN with ALT or AST ≤ 3.0 x ULN | INC424: Hold dose until resolved to ≤ grade 1, then: If resolved in ≤ 7 days, then maintain dose level If resolved in > 7 days, then ↓ by 5 mg BID LDE225: Hold dose until resolved to ≤ grade 1, then: If resolved in ≤ 7 days, then maintain dose If resolved in > 7 days, then ↓ 1 dose level |
| > 3.0 - 10.0 x ULN with ALT or AST ≤ 3.0 x ULN | INC424: Hold dose until resolved to ≤ grade 1, then: If resolved in ≤ 7 days, then maintain dose level If resolved in > 7 days, then discontinue treatment LDE225: Hold dose until resolved to ≤ grade 1, then ↓ 1 dose level |
| > 10.0 x ULN | INC424: Discontinue study treatment LDE225: Discontinue study treatment |
| AST or ALT | |
| Grade 1 (> ULN – 3.0 x ULN) | INC424: Maintain dose level LDE225: Maintain dose level |
| Grade 2 (> 3.0 - 5.0 x ULN) without total bilirubin elevation to > 2.0 x ULN | INC424: Maintain dose level LDE225: Maintain dose level |
| Grade 3 (> 5.0 - 20.0 x ULN) without total bilirubin elevation to > 2.0 x ULN | INC424: Hold dose until resolved to ≤ grade 1, then: If resolved in ≤ 7 days, then maintain dose level If resolved in > 7 days, then ↓ by 5 mg BID LDE225: Hold dose until resolved to ≤ grade 1, then ↓ 1 dose level |
| Grade 4 (> 20.0 x ULN) without bilirubin elevation to > 2.0 x ULN | INC424: Hold dose until resolved to ≤ grade 1, then ↓ by 5 mg BID LDE225: Hold dose until resolved to ≤ grade 1 or baseline, then ↓ 1 dose level |
| CARDIAC | |
| Cardiac – QTc prolongation | |
| QTcF > 500 ms (≥ Grade 3) or > 60 ms change from baseline on at least two separate ECGs | Perform an analysis of serum potassium and magnesium, and if below lower limit of normal, correct with supplements to within normal limits. Concomitant medication usage must be reviewed. Perform a repeat ECG within one hour of the first QTcF of > 500 ms. If QTcF remains > 500 ms, repeat ECG as clinically indicated but at least once a day until the QTcF returns to < 480 ms. INC424: Hold dose until QTcF prolongation has resolved, then ↓ by 5 mg BID LDE225: Hold dose. Once QTcF prolongation has resolved, study treatment may be restarted at ↓ 1 dose level Second Occurrence: Discontinue patient from further study treatment with both medications |
| Other non- hematological adverse events | |
| Grade 1 or 2 | INC424: Maintain dose level LDE225: Maintain dose level |

| | |
|---|--|

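### Table 6-4 has no hepatic row when ALT and AST both exceed 3 × ULN and bilirubin is above 2 and up to 10 × ULN; in one combination a written dose hold is lost

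*Protocol*

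**What the plan says.** Protocol section 6.3.1, Table 6-4, has two hepatic blocks.

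- **Bilirubin.** Up to 2 × ULN: maintain. Above 2 to 3 × ULN: hold both drugs, then restart at the same or a lower dose depending on whether recovery took more than 7 days. Above 3 to 10 × ULN: hold both; LDE225 restarts one level lower, and for INC424 "If resolved in > 7 days, then discontinue treatment". Above 10 × ULN: discontinue. Both middle rows are conditional on at least one enzyme being at most 3 × ULN ("3.0 x ULN with ALT or AST").
- **ALT/AST.** Grade 2, 3 and 4 rows exist, each restricted to patients without bilirubin above 2 × ULN: "Grade 2 (> 3.0 - 5.0 x ULN) without total bilirubin elevation to > 2.0 x ULN" (maintain), a matching Grade 3 row (hold), and "Grade 4 (> 20.0 x ULN) without bilirubin elevation to > 2.0 x ULN" (hold, then reduce).

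A later block, "Other non- hematological adverse events", says maintain for Grade 1–2, hold then reduce for Grade 3, and discontinue for Grade 4.

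Table 6-3 (section 6.2.5) makes three hepatic findings dose-limiting: "Total bilirubin CTCAE Grade" 3 or higher with direct bilirubin of at least 0.5 mg/dL, ALT/AST Grade 3 for at least 5 consecutive days, and "AST/SGOT or ALT/SGPT CTCAE Grade 4". Section 6.2.5 adds: "Patients who experience a DLT will have their therapy with LDE225 and INC424 interrupted". Sections 6.2.5 and 7.1.3 both list Grade 4 non-hematologic toxicity as a reason for permanent discontinuation.

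**The concern.** The two hepatic blocks exclude each other. When both enzymes and bilirubin are raised, the bilirubin rows drop out because the enzymes are high, and the enzyme rows drop out because bilirubin is high. That is the pattern in which a liver-safety table most needs to give an instruction.

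At stake is whether a dose hold rests on a rule or on judgement. Follow-up is affected too. Twice-weekly hepatic tests in Table 6-7 start after a hepatic DLT, and the weekly follow-up in section 6.3.2 starts after interruption or discontinuation. A patient with neither stays on the routine chemistry schedule: every 4 weeks from Week 13 and every 12 weeks in the extension. Table 6-7 does separately ask for bilirubin fractionation, and further assessment as indicated, whenever total bilirubin is above ULN. No efficacy endpoint, sample size or error rate is involved.

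**Working it through.** **Coding the rows.** All limits are those printed in Table 6-4, in multiples of ULN. Let b be total bilirubin, lo the lower and hi the higher of ALT and AST.

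- Bilirubin rows: b ≤ 2; 2 < b ≤ 3 and lo ≤ 3; 3 < b ≤ 10 and lo ≤ 3; b > 10.
- ALT/AST rows: 1 < hi ≤ 3; 3 < hi ≤ 5 and b ≤ 2; 5 < hi ≤ 20 and b ≤ 2; hi > 20 and b ≤ 2.

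No hepatic row applies when lo > 3 and 2 < b ≤ 10. That is 3 enzyme bands (> 3–5, > 5–20, > 20) × 2 bilirubin bands (> 2–3, > 3–10) = 6 combinations. The count describes the table; it is not a risk.

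**Spot checks**

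| Bilirubin | ALT / AST | Hepatic row | Action |
|---|---|---|---|
| 1.8 | 4 / 4 | ALT/AST Grade 2 | maintain |
| 2.5 | 2 / 2 | bilirubin > 2–3 | hold both |
| 2.5 | 4 / 2 | bilirubin > 2–3 | hold both |
| 2.5 | 4 / 4 | none | – |
| 2.5 | 10 / 10 or 25 / 25 | none | – |
| 6 | 4 / 2 | bilirubin > 3–10 | hold both |
| 6 | 4 / 4, 10 / 10 or 25 / 25 | none | – |
| 12 | any | bilirubin > 10 | discontinue |

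**What else covers the six combinations.** The protocol does not print CTCAE limits for bilirubin. I assume > 2–3 is Grade 2 and > 3–10 is Grade 3.

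1. *Enzymes > 20, either bilirubin band (two).* ALT/AST Grade 4 is a DLT, so treatment is at least interrupted. Discontinuation follows if the general Grade 4 rule covers liver enzymes.
2. *Enzymes > 5–20, bilirubin > 2–3 (one).* A hold through the catch-all Grade 3 row if it applies; otherwise a DLT interruption once Grade 3 has lasted 5 consecutive days.
3. *Enzymes > 3–5 or > 5–20, bilirubin > 3–10 (two).* A DLT if direct bilirubin is at least 0.5 mg/dL, so interruption and sponsor consultation apply. What is lost is the 7-day stopping rule for INC424, which through section 4.3.1 would stop both drugs. The 21-day rule in 6.3.1 remains, with its exception for patients who are responding.
4. *Enzymes > 3–5, bilirubin > 2–3 (one).* No hepatic DLT criterion is met. Either no row applies, or the catch-all Grade 1–2 row says maintain.

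2 + 1 + 2 + 1 = 6. Only the fourth item lacks a firm hold. Moving from 2.5 with 4 / 2 to 2.5 with 4 / 4, the second raised enzyme removes the written hold.

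**Sensitivity.** If bilirubin > 2–3 were Grade 3 and the catch-all applied, item 4 would be a hold. If the bilirubin condition means that both enzymes must be at most 3, the 4 / 2 patient also loses the hold row and the gap is wider.

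**The case against.** **Judgement covers the gap.** Section 6.3.1 bases modifications on the worst preceding toxicity and allows departures for safety. The Table 6-4 footnote allows case-by-case discussion with the sponsor. Section 7.1.3 tells the investigator to stop if continuing would be detrimental. This stands to the extent that patients are not left unmanaged. But none of these provisions names a hold for this patient, and the row that does excludes the patient.

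**The loss is not one-sided.** For bilirubin > 3–10, the missing row would let INC424 restart at the same dose after recovery within 7 days, whereas 6.3.1 requires a reduced combination dose after a DLT. This is right, and the fix must preserve the stricter restart.

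**Early treatment.** Table 6-4 bars modifications for treatment-related toxicity in the first 6 weeks until a DLT is reached. If a hold counts as a modification, the contrast in the fourth item applies only after that period.

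**Grade 4 ALT/AST.** A reader might infer that the protocol gives two opposite orders, restart in Table 6-4 and permanent stop in 6.2.5 and 7.1.3, and that stopping is the only correct resolution. For that reading: Table 6-3 places ALT/AST Grade 4 under non-hematologic toxicity, section 8.1.1 makes a laboratory value that changes dosing an adverse event, and neither list exempts liver enzymes. Against it: both lists name Grade 4 renal toxicity separately, which would be redundant if the general phrase were all-inclusive. CK elevation is also classed as non-hematologic in Table 6-3, yet Table 6-5 allows restart after Grade 4 CK without renal impairment, and 7.1.3 requires stopping only when renal impairment is present and values do not recover. The general phrase can therefore be read as residual. Section 1.4.1.2.1 also reports Grade 3 or 4 AST/ALT accompanying muscle toxicity, and 8 of 19 patients with Grade 3/4 CK elevation resuming at reduced doses without a further Grade 3/4 elevation. The text is ambiguous, not plainly contradictory.

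**Conclusion.** The gap holds on the printed text. Its practical core is one combination, both enzymes > 3–5 with bilirubin > 2–3 × ULN, where a hold written for milder enzyme elevation is lost. That no row is left needs only the literal wording. That the instruction becomes maintain needs two further assumptions: the catch-all row covers hepatic values, and this bilirubin is Grade 2.

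A reader might infer that all six combinations leave patients without protection. The documents do not support that: five are wholly or mostly covered by DLT, Grade 3/4 or discontinuation rules.

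Frequency is unknown. Table 1-3 gives suspected-related Grade 3/4 AST in 4/103 = 3.9% and ALT in 3/103 = 2.9% with single-agent LDE225, each 0/26 at 800 mg QD. These are neither joint elevations nor combination data, though they suggest a low rate. Correction is worthwhile because the edit is small and affects safety. The Grade 4 row is a separate ambiguity to clarify.

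**What to change.** In Table 6-4:

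- Delete the ALT/AST condition from the bilirubin > 2–3 and > 3–10 × ULN rows, so that they apply at any enzyme level as a minimum action.
- Delete the bilirubin condition from the ALT/AST Grade 2, 3 and 4 rows.
- Add: 'If both are raised, the stricter action applies; after a DLT the reduced-dose restart in 6.3.1 still applies.'
- Keep the use of direct bilirubin for Gilbert syndrome.

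In the same amendment, state whether the ALT/AST Grade 4 row or the general Grade 4 rule in 6.2.5 and 7.1.3 governs, taking account of muscle-derived AST/ALT and Table 6-5. This should be settled together, because removing the bilirubin condition extends the Grade 4 row to patients with raised bilirubin. Either answer is workable if it is written consistently in all three places.

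Cost: a protocol amendment with sponsor, ethics and, where required, Health Authority approval (section 12.1), and possibly a few more dose holds. No new tests are needed, since Table 7-6 already includes ALT, AST and bilirubin. Only patients still on treatment can benefit.

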| Cardiac | If \geq grade 3 (QTcF $>$ 500 msec as identified by the investigator on the ECG reading or $>$ 60 ms change from baseline on at least 2 separate ECGs taken within 1 hour): The patient must be hospitalized or monitored by the investigators with hourly ECGs until the QTcF is \leq 500 msec and $<$ 30 msec from baseline. Immediate attention to potassium and magnesium and other clinical factors such as oxygenation, ischemia, and the like will be addressed. A plasma sample should be drawn to assess the concentration of LDE225, magnesium and potassium at the time when the absolute QTcF $>$ 500 msec. Once QTcF prolongation has resolved, reinstate treatment according to Table 6-4 and perform ECG monitoring weekly. If the ECGs obtained in the first 6 weeks after dose reduction are without any QTcF $>$ 500 msec and QTcF change from baseline \geq 60 msec, then ECG monitoring should be performed every 4 weeks. |

[figure not shown]

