7.1.3 Discontinuation of Study Treatment

Patients may voluntarily discontinue from study treatment for any reason at any time. If a patient decides to discontinue from the study treatment, the investigator must make every effort (e.g., telephone, e-mail, letter) to determine the primary reason for this decision and record this information in the patient's chart and on the appropriate eCRF pages. Patients may be considered withdrawn if they state an intention to withdraw, fail to return for visits, or become lost to follow-up for any other reason.

The investigator should discontinue study treatment for a given patient if he/she believes that continuation would be detrimental to the patient's well-being.

Study treatment must be discontinued under the following circumstances:

- Emergence of the following adverse events:
 - Grade 3 or 4 hemorrhagic event of any kind
 - Grade 3 renal toxicity for ≥ 7 consecutive days
 - Grade 4 renal toxicity
 - Grade 4 non-hematologic toxicity
 - Second occurrence of QTcF > 500 ms (\geq Grade 3) or > 60 ms change from baseline on at least two separate ECGs
 - Patient requires or undergoes splenic irradiation
 - Patient requires or undergoes splenectomy
- Any of the following laboratory abnormalities:
 - Grade 4 anemia for ≥ 7 consecutive days despite PRBC transfusions
 - Febrile neutropenia (Grade ≥ 3) (ANC $< 1.0 \times 10^9/L$, with a single temperature of ≥ 38.3 °C or a sustained temperature of ≥ 38 °C for more than one hour)
 - Grade 3 or 4 serum creatinine
 - Bilirubin $> 10.0 \times ULN$
 - Grade 3 or 4 asymptomatic or symptomatic CK elevation with renal function impairment in which CK and creatinine levels do not return to baseline after interrupting treatment
- Pregnancy

- The following deviations from the prescribed dose regimen for LDE225 and INC424:
 - Interruption of study treatment for > 21 days, regardless of reason, from the intended day of the next scheduled dose. However, if the patient is obtaining clinical benefit in terms of response, the patient may continue treatment at the same or at a reduced dose following discussion between the investigator and Novartis.
 - If after 2 dose reductions and after the treatment has resumed at the lower dose, the same toxicity recurs with the same or worse severity (except for thrombocytopenia, anemia, and neutropenia)

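### Tables 6-4 and 6-7 end ECG monitoring of QTcF prolongation at different limits and frequencies, and neither defines the resolution on which restart of both drugs depends

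*Protocol*

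**What the plan says.** **Trigger.** Table 6-4 applies to QTcF above 500 ms, or to more than "60 ms change from baseline on at least two separate ECGs". Table 6-7 has the same 500 ms limb, but its second limb is more than "60 ms change from baseline on at least 2 separate ECGs taken within 1 hour". Table 6-4 has no one-hour condition.

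**Monitoring.** Table 6-4 says "Perform a repeat ECG within one hour of the first QTcF of > 500 ms". If the value remains above 500 ms, the site is to "repeat ECG as clinically indicated but at least once a day until the QTcF returns to" below 480 ms. Table 6-7 says "The patient must be hospitalized or monitored by the investigators with hourly ECGs until the QTcF is" at most 500 ms and also less than 30 ms from baseline.

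**Restart.** Table 6-4 holds both drugs until the prolongation has resolved and then restarts them at a reduced dose, with no number attached to the word. Table 6-7 says "Once QTcF prolongation has resolved, reinstate treatment according to" Table 6-4.

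**Stopping.** Table 6-4 discontinues both drugs at a second occurrence. Section 7.1.3 lists "Second occurrence of QTcF" above 500 ms, or the 60 ms change on two ECGs, among the reasons to discontinue. Sections 6.3.1 and 7.1.3 also require discontinuation after an interruption of more than 21 days, with an exception for patients in response after discussion with the sponsor.

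**The concern.** Two mandatory safety instructions address largely the same ECG finding and differ in what triggers them, how often to repeat the ECG, and when to stop repeating it. A site that obtains one ECG a day for a patient outside hospital complies with Table 6-4 and breaches Table 6-7.

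The restart rule then rests on a word that neither table defines. Table 6-7 sends the reader to Table 6-4 for reinstatement, and the QTc row there gives no threshold. Most other holds in Table 6-4 name the grade to which the toxicity must fall, and Table 6-5 names return to the baseline CK level. Without a stated meaning, two sites could end the hold on different days for the same tracings. Because hold length counts toward the 21-day rule, that date can also affect whether a patient has to leave treatment.

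**Working it through.** The plan states no figure to reproduce here. The check is whether the two end-of-monitoring limits ever disagree on the same ECG.

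**Inputs**
- Limit A (Table 6-4): Q < 480 ms, where Q is QTcF.
- Limit B (Table 6-7): Q ≤ 500 ms and Q − b < 30 ms, where b is baseline QTcF.
- Eligible screening QTcF (Section 5.3, exclusion 4): at most 450 ms in men and 470 ms in women. The lower baselines below are illustrative.

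**Where each limit is met, in whole milliseconds.** A is met up to 479. B is met up to the smaller of 500 and b + 29. For b ≤ 470, b + 29 ≤ 499, so the 30 ms condition is always the binding part of B.

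| Baseline b | A met up to | B met up to | Limits disagree at |
|---|---|---|---|
| 390 | 479 | 419 | 420–479 (A only) |
| 400 | 479 | 429 | 430–479 (A only) |
| 440 | 479 | 469 | 470–479 (A only) |
| 450 | 479 | 479 | nowhere |
| 460 | 479 | 489 | 480–489 (B only) |
| 468 | 479 | 497 | 480–497 (B only) |
| 470 | 479 | 499 | 480–499 (B only) |

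The limits coincide only at b = 450, since 450 + 30 = 480. Below that, A is met first; above it, within the range open only to women, B is met first. Neither limit implies the other.

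**The 60 ms trigger.** A change of more than 60 ms first occurs at Q = b + 61. This is already below 480 when b + 61 ≤ 479, that is, when b ≤ 418. At b = 400, for example, two ECGs at 465 ms (+65 ms) meet the Table 6-4 trigger with QTcF already under 480 ms. They also meet the Table 6-7 trigger if taken within one hour. The 480 ms limit cannot mark the end of such an event. In any case, the repeat-ECG steps in Table 6-4 are written only for values above 500 ms, so that table offers no ECG end point for this trigger. Table 6-7 would require Q < 430.

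**Restart.** Setting the two rows side by side, the hold in each ends on resolution, and neither attaches a number to it. The 480 ms limit and the 500/30 ms pair are the only candidates in the rows, and the table above shows that they can disagree on the same ECG.

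**The case against.** The case against is substantial, and parts of it stand.

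- A reader might infer that the two frequencies cannot both be followed, or put a ratio on them. The text does not support this. The daily figure in Table 6-4 is a minimum, and hourly ECGs satisfy it, so a site that monitors to the later of the two end points complies with both tables.
- A reader might take 480 ms and 500/30 ms as rival definitions of resolution. Both are written only as ends of ECG repetition. The defect is an undefined term with two candidates, not two stated definitions.
- A reader might infer that the second-occurrence stop depends on resolution. Table 6-4 and Section 7.1.3 never say so; Section 7.1.3 words the stop on the trigger being met again.
- A reader might infer that a forced stop makes the patient a non-responder. Section 7.1.3 says that patients who stop treatment are not withdrawn from the study and should return for assessments. Protocol Section 10.4.3 and SAP Section 3.5.3 attach non-response to missing assessments, study drop-out or progression.
- Section 6.3.1 has dosing adjustments discussed with the sponsor, which gives an informal route to a decision. It also asks for recovery to grade 1 or baseline after a dose-limiting toxicity. That sentence covers only events that qualify as such, and the documents do not translate the grade into milliseconds.
- Events should be rare. Section 1.4.1.2.1 reports no clinically significant ECG changes in the phase I study of LDE225, and Section 1.4.2.2.1 reports no adverse ECG effect of INC424 in a dedicated QT study. Both are single-agent data.

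None of this tells a site which end point closes the event or when the hold ends. Section 6.3.1 does not settle precedence either: it refers hematologic, renal and hepatic toxicities to Table 6-7 but does not mention its cardiac row.

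**Conclusion.** The point holds as an internal inconsistency in a safety instruction. The two rows differ in trigger wording, ECG frequency and end-of-monitoring limit. Table 6-4 leaves the 60 ms trigger without an end point, and the resolution that governs restart of both drugs is undefined.

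The range of disagreement depends on baseline: 50 ms-values at 400 ms (430 to 479), 18 at 468 ms (480 to 497), and none at 450 ms. It has no fixed maximum, because it widens as baseline falls. These ranges assume that the baseline used for change lies within the screening limits. SAP Section 3.8.4.1 averages all pre-dose ECGs, so an individual baseline could differ from the screening value.

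The documents do not allow an expected number of affected patients to be calculated, and no effect on the primary endpoint is claimed. The only consequence tied to the text beyond restart is that hold time counts toward the 21-day rule, subject to its response exception. The point is worth correcting because it concerns patient safety and is cheap to resolve. It implies no view on which limit is right.

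**What to change.** Reconcile the cardiac rows of Tables 6-4 and 6-7 so that the trigger (including whether the one-hour condition applies), the monitoring frequency, the end of monitoring and the meaning of resolution agree for both the 500 ms and the 60 ms triggers. If a stepped scheme with two end points is intended, the rows should say so. Check that Section 7.1.3 is consistent with the result. All values and clinical rules are for the sponsor's clinical team to set.

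The cost is amendment wording in two table rows and one cross-check. Aligning the rows need not add any procedure that one of the tables does not already require.
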